8.5.2 DEFINITION OF SERIOUS ADVERSE EVENTS

A serious adverse event (SAE) will be considered any undesirable sign, symptom, or medical condition which is fatal, is life-threatening, requires or prolongs inpatient hospitalization, results in persistent or significant disability/incapacity, constitutes a congenital anomaly or birth defect, is medically significant

and which the investigator regards as serious based on appropriate medical judgment. An important medical event is any AE that may not result in death, be life-threatening, or require hospitalization but may be considered an SAE when, based upon appropriate medical judgment, it may jeopardize the patient and may require medical or surgical intervention to prevent one of the outcomes listed in the definitions of SAEs. As with the definition of AEs provided in 8.5.1, this protocol defines a SAE as an SAE that is definitely, probably, or possibly related to the study intervention (see 8.5.3).

8.5.3 CLASSIFICATION OF AN ADVERSE EVENT

8.5.3.1 SEVERITY OF EVENT

The following guidelines will be used to describe AE severity.

- **Mild** – Events require minimal or no treatment and do not interfere with the participant's daily activities.
- **Moderate** – Events result in a low level of inconvenience or concern with the therapeutic measures. Moderate events may cause some interference with functioning.
- **Severe** – Events interrupt a participant's usual daily activity and may require systemic drug therapy or other treatment. Severe events are usually potentially life-threatening or incapacitating. Of note, the term "severe" does not necessarily equate to "serious".

8.5.3.2 RELATIONSHIP TO STUDY INTERVENTION

All AEs will have their relationship to study procedures, including the intervention, assessed by the PI based on temporal relationship and his clinical judgment. The degree of certainty about causality will be graded using the categories below.

- **Definitely Related** – There is clear evidence to suggest a causal relationship, and other possible contributing factors can be ruled out. The clinical event, including an abnormal laboratory test result, occurs in a plausible time relationship to study procedures administration and cannot be explained by concurrent disease or other drugs or chemicals. The response to withdrawal of the study procedures should be clinically plausible. The event must be pharmacologically or phenomenologically definitive.
- **Probably Related** – There is evidence to suggest a causal relationship, and the influence of other factors is unlikely. The clinical event, including an abnormal laboratory test result, occurs within a reasonable time after administration of the study procedures, is unlikely to be attributed to concurrent disease or other drugs or chemicals, and follows a clinically reasonable response on withdrawal.
- **Possibly Related** – There is some evidence to suggest a causal relationship (e.g., the event occurred within a reasonable time after administration of study procedures). However, other factors may have contributed to the event (e.g., the participant's clinical condition, other concomitant events). Although an AE may rate only as "possibly related" soon after discovery, it can be flagged as requiring more information and later be upgraded to "probably related" or "definitely related", as appropriate.

8.5.3.3 TIME PERIOD AND FREQUENCY FOR EVENT ASSESSMENT AND FOLLOW-UP

Recording/reporting of AEs will begin after the subject signs informed consent and end after the subject completes the intervention and follow up period as defined in the protocol.

8.5.3.4 ADVERSE EVENT REPORTING

All AEs, as defined above, will be collected and reported. Data collection will occur via electronic spreadsheet. The information will be saved in REDCap and managed by the study team. In consultation with the PI, a trained member of the study team will be responsible for conducting an evaluation of a SAE and shall report the results of such evaluation to the NIH and the reviewing Institutional Review Board (IRB) as soon as possible and in accordance with the reviewing IRB policy

8.5.3.5 SERIOUS ADVERSE EVENT REPORTING

In consultation with the PI, a trained member of the study team will be responsible for conducting an evaluation of a SAE and shall report the results of such evaluation to the NIH and the reviewing IRB as soon as possible and in accordance with the reviewing IRB policy.

8.5.3.6 REPORTING EVENTS TO PARTICIPANT

N/A

8.5.3.7 EVENTS OF SPECIAL INTEREST

N/A

8.5.3.8 REPORTING OF PREGNANCY

N/A

8.6 UNANTICIPATED PROBLEMS**8.6.1 DEFINITION OF UNANTICIPATED PROBLEMS**

This protocol uses the definition of Unanticipated Problems (UP) as defined by the Office for Human Research Protections (OHRP). OHRP considers unanticipated problems involving risks to participants or others to include, in general, any incident, experience, or outcome that meets all of the following criteria:

- Unexpected in terms of nature, severity, or frequency given (a) the research procedures that are described in the protocol-related documents, such as the IRB-approved research protocol and informed consent document; and (b) the characteristics of the participant population being studied;
- Related or possibly related to participation in the research (“possibly related” means there is a reasonable possibility that the incident, experience, or outcome may have been caused by the procedures involved in the research); and
- Suggests that the research places participants or others at a greater risk of harm (including physical, psychological, economic, or social harm) than was previously known or recognized.

8.6.2 UNANTICIPATED PROBLEMS REPORTING

The investigator will report UPs to the reviewing IRB and to the lead PI. The UP report will include the following information:

- Protocol identifying information: protocol title and number, PI's name, and the IRB project number
- A detailed description of the event, incident, experience, or outcome

- An explanation of the basis for determining that the event, incident, experience, or outcome represents an UP
- A description of any changes to the protocol or other corrective actions that have been taken or are proposed in response to the UP

To satisfy the requirement for prompt reporting, UPs will be reported using the following timeline:

- Ups will be reported to the IRB and to the NCI in accordance with policy regarding timeliness of reporting
- All UPs should be reported to appropriate institutional officials (as required by an institution's written reporting procedures), the supporting agency head (or designee), and the OHRP in accordance with policy regarding timeliness

9 STATISTICAL CONSIDERATIONS

9.1 STATISTICAL HYPOTHESES

9.1.1 SINGLE ARM FEASIBILITY STUDY

NDURE Accrual (Primary Endpoint)

We hypothesize that at least 60% of eligible subjects for the NDURE study will accrue to the study. Alternatively, our null hypothesis is that less than 60% of eligible subjects for the NDURE study will accrue to the study.

The preliminary feasibility analysis will be calculated for the secondary endpoint using the first 25 patients eligible to accrue to the study, which is expected to occur over 4 months.

NDURE Completion (Secondary Endpoint)

We hypothesize that at least 85% of subjects who enroll in the NDURE study (at least 13 of 15 subjects) will complete all 3 NDURE sessions. Alternatively, our null hypothesis is that less than 13 of the 15 subjects who enroll in the NDURE study will complete all 3 NDURE sessions

The preliminary feasibility analysis will be calculated for the secondary endpoint using the first 15 patients who accrue to the study, which is expected to occur over 6 months.

9.1.2 RCT OF NDURE VERSUS USUAL CARE

PORT Delay (Primary Endpoint)

We hypothesize that, compared with patients who receive usual care, patients who receive NDURE will have a decreased rate of PORT delay (initiation of PORT > 6 weeks after surgery). Alternatively, our null hypothesis is that there will be no difference in the rate of PORT delay between NDURE and usual care.

PORT Delay (Secondary Endpoint)

We hypothesize that, compared with usual care, NDURE will result in a smaller difference in the rate of PORT delay (initiation of PORT > 6 weeks after surgery) between AA and white patients. Alternatively, our null hypothesis is that there will be no difference in the rate of PORT delay between AA and white patients between NDURE and usual care.

TTP (Secondary Endpoint)

We hypothesize that, compared with patients who receive usual care, patients who receive NDURE will have a shorter median TTP (time, in days, between the date of definitive surgical resection to the initiation of PORT). Alternatively, our null hypothesis is that there will be no difference in median TTP between NDURE and usual care.

TTP (Secondary Endpoint)

We hypothesize that, compared with usual care, NDURE will result in a smaller difference in the median TTP between AA and white patients. Alternatively, our null hypothesis is that there will be no difference in the median TTP between AA and white patients between NDURE and usual care.

9.2 SAMPLE SIZE DETERMINATION

9.2.1 NDURE FEASIBILITY STUDY

Power and sample size calculations were performed using the University of Iowa Binomial Distribution applet. The sample size justification for this single-arm study is based on the primary feasibility endpoints of NDURE accrual and completion. In the RCT of NDURE, we plan to enroll 60% of eligible patients. We expect similar accrual in this feasibility study. Therefore, we hypothesize that at least 60% of eligible subjects for the NDURE study will accrue to the study. Alternatively, our null hypothesis is that less than 60% of eligible subjects for the NDURE study will accrue to the study. Accruing to NDURE will be considered feasible if at least 15 of 25 eligible subjects enroll. Our sample size for the feasibility study was selected to provide a small probability of having an observed accrual rate of at least 60% when the true accrual probability is actually less than 60%. For example, if the true accrual probability for our proposed design is 45% (35%), the probability of enrolling 15 or more of 25 eligible subjects is only 10% (1%). Additionally, we hypothesize that at least 85% of subjects who enroll in the NDURE study will complete all 3 NDURE sessions. Alternatively, our null hypothesis is that less than 85% of subjects who enroll in the NDURE study will complete all 3 NDURE sessions. That is to say, NDURE will be considered feasible if at least 13 of the 15 subjects enrolled complete all three NDURE sessions. Accordingly, our sample size for the single-arm study was selected to provide a small probability of having an observed completion rate of at least 85% when the true completion probability of the intervention is actually less than 85%. For example, if the true completion probability for our proposed design is 70% (60%), the probability that 13 or more of the 15 enrolled patients complete all three NDURE sessions is 13% (3%). Therefore, the probability of falsely declaring NDURE feasible is reasonably controlled based on this sample size.

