Abbreviations: CASE: Communication & Attitudinal Self-Efficacy Scale; CT: Computed Tomography; CTM-15: Care Transition Measures-15; d: days; IPQ-R: Illness Perception Questionnaire-Revised; ISEL-12: Interpersonal Support Evaluation List-12; NDURE: Navigation for Disparities and Untimely Radiation ThErapy; PBQ: Perceived Barriers Questionnaire; PORT: Postoperative Radiation Therapy; PSN-I: Patient Satisfaction with the Interpersonal Relationship with the Navigator Scale; PSQ: Perceived Susceptibility Questionnaire; Rad Onc: Radiation therapy RT: Radiation therapy								
^a If the discharge date is expected to be > 21 days after surgery, then complete all Study Visit 3 assessments (except CTM-15) on postoperative day 21. If the patient is unable to complete the assessments on postoperative day 21 (due to mental status), then complete on the 1 st day after postoperative day 21 in which the mental status allows completion of the assessments. If the patient is subsequently discharged after postoperative day 21, then the CTM-15 can be completed on the time of discharge. If the patient is never discharged prior to PORT, then the CTM-15 is omitted.								
^b For patients undergoing transoral robotic surgery and staged neck dissection, Study Visit 3 assessments should be completed after the second hospitalization (regardless of the order of transoral robotic surgery and the neck dissection).								
^c If the participant is never discharged from the hospital postoperatively prior to starting PORT, Study Visit 4 intervention and assessments are omitted.								

Table 1. Schedule of Activities for NDURE and Usual Care: Screening, Treatment, and Follow-up							
Study Period	Screening	Allocation	Treatment				Follow-Up
			Pre -Op	Pre - D/ C	Post - D/C	Start of PORT	
Visit Label			1	2	3 ^{a,b}	4 ^c	5 ^d
Visit #							6 ^e
Study Activity							

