7.2 PARTICIPANT DISCONTINUATION/WITHDRAWAL FROM THE STUDY

Participants are free to withdraw from participation in the study at any time upon request. The investigators will seek to minimize participant discontinuation/withdrawal from the study (see Section 7.3, Lost to Follow-Up) except for safety reasons.

The investigator may discontinue a participant from the study for the following reasons:

- Significant study intervention non-compliance

- Lost-to-follow up; unable to contact subject (see **Section 7.3, Lost to Follow-Up**)
- Any event or medical condition or situation occurs such that continued collection of follow-up study data would not be in the best interest of the participant or might require an additional treatment that would confound the interpretation of the study
- The participant is expected to have surgery and then decides to pursue (1) nonsurgical treatment or (2) surgical treatment at a site not participating in the clinical trial
- PORT is expected based on the clinical TNM classification, but analysis of the pathology specimen after surgery demonstrates no indication for PORT per NCCN Guidelines (i.e., all of the following adverse features are absent: extranodal extension, positive margin, pT3 or pT4 primary, N2 or N3 nodal disease, nodal disease in levels IV or V, PNI, and LVI)

The date and reason for participant discontinuation or withdrawal from the study will be recorded in the eCRF.

The reason for participant discontinuation or withdrawal from the study will be recorded on the eCRF.

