trial arms will be analyzed using a model-based approach (discussed in Section 9.4.3.2) with inclusion of randomization stratification variables as model covariates, an analytic approach which preserves the type I error rate at nominal α , and increases power relative to an unadjusted model.⁶¹ Therefore, our power analysis based on a Z-test is conservative, and we anticipate even greater power based on our analytic plan. We therefore consider our RCT to be appropriately and rigorously designed to detect a clinically meaningful reduction in PORT delay. In order to have 150 patients eligible for the PORT delay analysis set (see Section 9.3, Population for Analyses), we plan to enroll 170 patients. Our sample size is inflated by 17% based on historical data. If at 170 patient accruals we have not achieved 75 patients evaluable for the primary endpoint in each arm, we will continue to enroll until we have achieved either accrual of a minimum of 75 evaluable patients in each arm or have accrued a maximum of 180 total patients.

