9.3 POPULATIONS FOR ANALYSES

The safety analysis set (SAS) is composed of all patients enrolled who receive any part of either the NDURE or UC intervention. The SAS will be used to conduct all safety analyses. Patients will be analyzed based on the intervention received regardless of the assignment at randomization.

The PORT delay analysis set is composed of all patients enrolled in the trial who are:

1. Randomized to NDURE or UC
2. Receive curative intent surgery at MUSC
3. Have an indication for PORT per NCCN Guidelines based on the presence of at least one of the following adverse features on final pathologic evaluation: ENE, positive margin, pT3 or pT4 primary, at least pN1 nodal disease (per AJCC 8th edition for p16-ve non-oropharyngeal SCC or AJCC 7th edition for p16+ve oropharyngeal SCC), nodal disease in levels IV or V, PNI or LVI
4. Are alive for ≥ 6 weeks postoperatively.

Analysis will be performed based on assignment at randomization regardless of the intervention received (modified intent to treat). This analysis set will be used for analysis of the primary endpoint. The rationale for this definition of the PORT delay evaluable set is that eligibility, randomization, and delivery of a portion of the intervention occur prior to definitive treatment of the HNSCC. However, the primary endpoint is evaluable only for patients who undergo surgery for HNSCC, have an indication for adjuvant PORT (which can only be definitively known following surgical resection), and are alive for at least 6 weeks postoperatively. Therefore, we expect that a subset of patients who meet all eligibility criteria will be enrolled in the study, randomized to NDURE or UC, receive a portion of the intervention, but subsequently be non-evaluable for the primary endpoint when information becomes available later in the clinical course that cannot be known at the time of study enrollment and randomization (e.g., they (1) elect a non-surgical treatment option; (2) have no indication for PORT per NCCN Guidelines on final pathologic assessment; (3) have a mortality prior to 6 weeks postoperatively).

The Time-to-PORT (TTP) analysis set is composed of all patients enrolled in the trial who are:

1. Randomized to NDURE or UC
2. Receive curative intent surgery at MUSC

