9.4.4 ANALYSIS OF THE SECONDARY ENDPOINTS

9.4.4.1 NDURE FEASIBILITY STUDY

NDURE completion rate will be analyzed as 1) the percentage of enrolled patients who attend all three NDURE sessions and 2) the proportion of three NDURE sessions that are completed. For navigator caseload, we will consider the frequency of simultaneous cases navigated. Navigator time allocation for direct and indirect time, as well as patient-report measures of satisfaction with navigation will be summarized as described above for continuous data. Study questionnaire completion rate will be calculated as the proportion of pre- and post-intervention questionnaires (n=5 each) completed. Qualitative data will be analyzed using established team codebooks and focus on the content, format, delivery, and timing of NDURE. Qualitative analysis of semi-structured interviews with patients and providers following the pilot will be analyzed using established codebooks from the study team for evaluating the feasibility and acceptability of clinic-based HNSCC interventions with a focus on the content, format, delivery, and timing of NDURE.

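### The 13-of-15 completion rule scores patients who could not receive all three sessions as NDURE failures, conflicts with the completion definition in 8.4.1, and states no false-fail risk

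*Combined protocol and SAP*

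**What the plan says.** Section 9.2.1 sets the target that "at least 85% of subjects who enroll in the NDURE study will complete all 3 NDURE sessions" and turns it into a decision rule: "NDURE will be considered feasible if at least 13 of the 15 subjects enrolled complete all three NDURE sessions". Section 9.1.1 makes the assessment "using the first 15 patients who accrue to the study", and 9.4.4.1 analyses "the percentage of enrolled patients who attend all three NDURE sessions". None of the three sections limits the count to patients who remained on the surgery-plus-PORT pathway.

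Other sections describe patients who cannot receive all three sessions, or may not:

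- Sessions 2 and 3 coincide with hospital discharge and the first postoperative clinic visit (4.2.3.2, 6.1.2.1), so they require surgery at MUSC and survival to that visit.
- Schedule of Activities (1.3), footnote c: "If the participant is never discharged from the hospital postoperatively prior to starting PORT, Study Visit 4 intervention and assessments are omitted". Visit 4 is session 3.
- Section 7.2 allows discontinuation when "The participant is expected to have surgery and then decides to pursue (1) nonsurgical treatment", when surgery takes place elsewhere, or when pathology shows no indication for PORT.
- For the RCT, 9.3 says "we expect that a subset of patients who meet all eligibility criteria will be enrolled in the study" and later become non-evaluable, and it removes them from the primary analysis set. Section 9.2.2 allows for them: "Our sample size is inflated by 17% based on historical data".

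Section 8.4.1 defines the completion rate differently: the baseline assessment, two or more sessions, and the final follow-up assessment.

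**The concern.** The rule is meant to show whether NDURE can be delivered. As written, it also measures how many of 15 patients changed treatment plan, died early, or stayed in hospital until PORT, none of which shows whether the navigator could deliver a session that was due. Three such patients produce a not-feasible result even if every session that fell due was delivered.

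The protocol anticipates these exits for the RCT and adjusts its analysis set and enrolment, yet makes no matching provision in the feasibility rule, which uses the same eligibility criteria. Section 9.2.1 quotes only the probability of passing when true completion is low, so a reader cannot see how often the rule fails a deliverable intervention. In addition, a patient with two sessions and an omitted Visit 4 can be a completer under 8.4.1 and a non-completer under 9.1.1, 9.2.1 and 9.4.4.1.

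**Working it through.** **1. The plan's own figures.** For 15 enrolled and a cut-off of 13, the probability of passing at true completion p is the exact binomial tail

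P(pass) = Σ (k = 13 to 15) C(15,k) p^k (1−p)^(15−k).

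At p = 0.70 this is 12.7%, and at p = 0.60 it is 2.7%. Section 9.2.1 states 13% and 3%, so its figures reproduce.

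**2. The error not reported.** At p = 0.85, exactly on target, P(pass) = 60.4%, so the rule fails 39.6% of the time. At p = 0.95 it fails 3.6%.

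**3. A guide to the exit share.** The documents give no frequency for missed sessions. The nearest figure is the RCT's non-evaluable share d in 9.2.2:

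- 170 enrolled for 150 evaluable: d = 20/170 = 11.8%.
- 17% read as inflation: 150 × 1.17 = 175.5, so d = 1 − 1/1.17 = 14.5%.
- Maximum of 180 enrolled: d = 30/180 = 16.7%.
- 17% read as a loss rate: d = 17%.

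The range used is 11.8% to 17%. It is only a guide. Some RCT-non-evaluable patients may attend all three sessions. Conversely, patients covered by footnote c do start PORT, so they are not part of this share and would add to it.

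**4. False-fail risk under the current rule.** Let s be the fraction of non-evaluable patients who miss at least one session, and assume perfect delivery to everyone else. Then p = 1 − d·s and P(fail) = 1 − P(pass).

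| s | p at d = 11.8% | P(fail) | p at d = 17% | P(fail) |
|---|---|---|---|---|
| 1/3 | 0.961 | 1.9% | 0.943 | 5.0% |
| 1/2 | 0.941 | 5.4% | 0.915 | 12.9% |
| 2/3 | 0.922 | 10.8% | 0.887 | 23.7% |
| all | 0.882 | 25.5% | 0.830 | 48.2% |

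If exits are not counted as failures, perfect delivery fails 0% of the time by construction.

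**5. The rule applied to patients due.** With m patients for whom all three sessions fell due, the cut-off is the smallest whole number at or above 0.85m.

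| Due (m) | Cut-off | Pass at 70% | Pass at 85% | Pass at 95% |
|---|---|---|---|---|
| 12 | 11 | 9% | 44% | 88% |
| 13 | 12 | 6% | 40% | 86% |
| 14 | 12 | 16% | 65% | 97% |
| 15 | 13 | 13% | 60% | 96% |

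The false-pass risk at a true 70% therefore runs from 6% to 16%, depending on m. Averaged over a binomial number due from 15 enrolled, with exit rates from 5% to 17%, it is about 11% to 13%, against 12.7% now.

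**The case against.** **Completion among all enrolled patients is a legitimate, conservative measure.** NDURE starts before surgery. That stands, which is why the all-enrolled figure should still be reported. It does not justify using that figure alone to judge deliverability.

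**Being non-evaluable for PORT delay is not the same as missing a session.** A patient with no PORT indication has had surgery and may return for the first postoperative visit; discontinuation under 7.2 is optional; a death before six weeks can follow session 3. This stands, and it is why the result is a range. A reader might infer that the rule easily fails a fully deliverable intervention, or fails 45% to 64% of the time. The documents do not support that: it needs every non-evaluable patient to miss a session, and the 45% to 64% also needs a 95% delivery rate that the plan does not give.

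**A reader might also infer an 83% ceiling on completion, below the 85% target.** That holds only if 17% is a loss rate and all of those patients miss a session. Read as inflation, the ceiling is 85.5%; from 150 of 170 it is 88.2%.

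**Section 8.4.1 would spare a patient whose only missed session was an omitted Visit 4.** True, but it contradicts the three sections that state and analyse the rule, and a patient who never has surgery at MUSC still fails under it.

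**Section 4.2.3.2 expects almost all patients to attend the three visits.** Its argument rests on patients having surgery, so it does not cover those who do not. The replacement provision in 9.3 covers only drop-out before any intervention.

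**The rule is not a stated gate.** Completion is secondary in 9.1.1, although 9.2.1 lists it among the primary feasibility endpoints. No section makes the RCT conditional on 13 of 15, and 4.1.2 uses the feasibility data to refine the intervention. This stands and limits the consequence.

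**Conclusion.** The structural point holds: the rule as written counts patients who could not receive all three sessions as NDURE failures, tolerates only two non-completers, conflicts with 8.4.1, and comes with no false-fail risk.

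The size is uncertain because the documents do not give the share of patients who miss a session for these reasons. With the RCT's 11.8% to 17% as a guide and perfect delivery otherwise, the chance of a wrong not-feasible result is about 2% to 5% if one third of those patients miss a session, 5% to 13% if half do, and 26% to 48% if all do. These figures treat patients as independent and leave out footnote c omissions, whose frequency is not given. The plan should be corrected, but it does not follow that the rule will usually fail, or that failing would stop the RCT.

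**What to change.** 1. Reconcile 8.4.1 with 9.1.1, 9.2.1 and 9.4.4.1 so that there is one completion definition, and state how an omitted Visit 4 is counted.
2. Apply the 85% criterion to enrolled patients for whom all three sessions fell due. Define this by objective events only: surgery at MUSC, and alive and discharged before PORT. Do not use discontinuation under 7.2, which is discretionary and, in an unblinded single-arm study, would let the investigator influence who counts.
3. Report completion out of all 15 enrolled alongside, with the number of pathway exits and the reason for each.
4. State the cut-off as the smallest whole number at or above 85% of those due. Give pass probabilities for 12 to 15 due at true rates of 70%, 85% and 95%, as in the second table above.

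The cost is protocol wording and a short binomial table; no extra patients are needed. The downside is that the denominator is not fixed in advance and the false-pass risk varies with it: at a true 70% it is 16% with 14 due, against 13% under the current rule. The change also does not cure the low precision at the target itself, where the pass probability is only 40% to 65%.

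### The feasibility rules do not control false declarations against the stated nulls of accrual below 60% and completion below 85%; the examples given show control only near 45% and 70%

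*Combined protocol and SAP*

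**What the plan says.** Section 9.1.1 states for accrual that "our null hypothesis is that less than 60% of eligible subjects for the NDURE study will accrue to the study", and section 9.2.1 repeats it. The decision rule in section 9.2.1 is: "Accruing to NDURE will be considered feasible if at least 15 of 25 eligible subjects enroll". The stated purpose of the sample size is a "small probability of having an observed accrual rate of at least 60% when the true accrual probability is actually less than 60" per cent.

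For completion, section 9.2.1 says that "our null hypothesis is that less than 85% of subjects who enroll in the NDURE study will complete all 3 NDURE sessions", with the rule that "NDURE will be considered feasible if at least 13 of the 15 subjects enrolled complete all three NDURE sessions". It again claims a small probability of an "observed completion rate of at least 85% when the true completion probability of the intervention is actually less than 85" per cent. Section 9.1.1 words the completion null differently, as an observed count of fewer than 13 of 15.

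The support consists of four worked examples. The accrual rule passes with probability 10% at a true 45% and 1% at a true 35%. The completion rule passes with probability 13% at a true 70% and 3% at a true 60%. From these the section concludes that "the probability of falsely declaring NDURE feasible is reasonably controlled based on this sample size". It gives no numerical error rate for either rule and names no separate unacceptable rate below the 60% and 85% targets.

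**The concern.** Each null covers every true rate below the target, and each rule passes as soon as the observed rate reaches that target. When the pass mark sits on the edge of the null, a true rate just inside the null passes about half the time or more. The examples avoid this region: they lie 15 and 25 percentage points below each target. The conclusion about false declarations is therefore drawn for a much wider null than the examples cover.

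What is at stake is how a pass is read. Section 5.5 says that the 60% accrual target for the randomized trial will have been tested in the single-arm study. A reader who accepts the control claim would take 15 of 25 as good evidence that true accrual is at least 60%, and 13 of 15 as good evidence that completion is at least 85%. Neither result gives that.

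**Working it through.** **Inputs (section 9.2.1).** Accrual: n = 25, pass if X ≥ 15, null p < 0.60. Completion: n = 15, pass if X ≥ 13, null p < 0.85.

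**Cut-offs against the targets.** 15/25 = 60.0%, exactly the accrual target. 13/15 = 86.7% and 12/15 = 80.0%, so 13 is the smallest count that reaches 85%.

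**Formula.** P(pass) = P(X ≥ r) = Σ from k = r to n of C(n,k) p^k (1−p)^(n−k), with X binomial(n, p).

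**The plan's own figures.**

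| Rule | True rate | Plan | Exact |
|---|---|---|---|
| ≥15/25 | 45% | 10% | 9.6% |
| ≥15/25 | 35% | 1% | 0.9% |
| ≥13/15 | 70% | 13% | 12.7% |
| ≥13/15 | 60% | 3% | 2.7% |

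All four reproduce.

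**The same formula over the rest of the stated nulls.**

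| Accrual, true rate | P(≥15/25) | Completion, true rate | P(≥13/15) |
|---|---|---|---|
| 50% | 21.2% | 75% | 23.6% |
| 55% | 38.4% | 80% | 39.8% |
| 59% | 54.5% | 84% | 56.1% |
| 60% (limit) | 58.6% | 85% (limit) | 60.4% |

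The pass probability rises with p, so the last row is the largest false-declaration probability under each null. The same row is also the probability of passing when the true rate is exactly on target.

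**Where the rules do hold error to 10%.** Solving P(pass) = 0.10 gives a true accrual of about 45% and a true completion of about 68%.

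**What control at the stated boundaries would take with the same n.** For error of 10% or less, accrual would need 19/25 (7.4% at a true 60%; 18/25 gives 15.4%) and completion 15/15 (8.7% at a true 85%). These show the size of the gap and are not a proposal.

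**What a bare pass shows.** Exact (Clopper-Pearson) 90% confidence intervals: 15/25 gives 42% to 76%; 13/15 gives 64% to 98%.

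**What the randomized trial needs (sections 5.5 and 9.2.2).** With 375 screened over 36 months:
- 150 patients: 150/375 = 40%.
- 170 enrolled: 170/375 = 45%.
- 180 enrolled: 180/375 = 48%.
- White patients: 100/292 = 34%.
- African American patients: 50/83 = 60%, or 50/96 = 52% with the six-month extension.

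**The case against.** The strongest reply is that the plan discloses the true rates it evaluated, presents them as examples, sets no alpha, and uses a qualitative phrase. Section 9.1.1 even gives the completion null as a count, and sections 9.4.3.1 and 9.4.4.1 plan only descriptive summaries. On this view the rules are descriptive benchmarks. That bears on how much the point matters, but it does not make the claim true: section 9.2.1 names the nulls as below 60% and below 85% and says that passing is improbable under them.

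Four stronger readings are tempting, and the documents do not support them.

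- **That the plan miscalculated.** It did not; all four figures are right. The fault lies in the inference drawn from them.
- **That the randomized trial's accrual rests on 60%.** Overall enrolment needs about 40% to 48%. Mainly the African American projection needs 60%, and section 5.5 already plans recruitment refinement and an extension, after which 52% suffices. Section 9.4.3.1 also says that the study is not designed to evaluate racial differences in accrual.
- **That these are binding stop/go gates.** The plan says only what will be considered feasible; no section stops the randomized trial if a rule fails.
- **That both criteria together rescue the claim.** No joint rule is stated. If both had to be met and were independent, the pass probability would be 0.384 × 0.398 = 15% at 55%/80% and 0.545 × 0.561 = 31% at 59%/84%. If only one rate were deficient and the other nearly certain to pass, it would return to the single-criterion figure.

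**Conclusion.** The point stands as a stated property that the design does not have: wrong as written, but not an arithmetic error. Taken separately, the rules can pass with probability up to about 59% (accrual) and 60% (completion) under the nulls as written. The evidence in section 9.2.1 supports control only against about 45% accrual and 70% completion.

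This rests on independent patients with a common rate for each criterion, the same binomial model that the plan uses. The consequence is modest. This is a 15-patient single-arm study, the randomized trial's primary analysis, alpha and power are unaffected, and the recruitment projection most exposed to a shortfall from 60% already has a contingency. What needs correcting is the reading of a pass as confirmation of 60% or 85%.

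**What to change.** Keep the sample size, both cut-offs and the 60% and 85% targets. In sections 9.1.1 and 9.2.1:

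1. Restate the null (unacceptable) rates as 45% accrual and 70% completion, with false-declaration probabilities of 9.6% and 12.7%. Express the completion null as a true rate in both sections, replacing the observed count in 9.1.1.
2. Remove the claim of control against any rate below 60% or 85%.
3. State that the pass probability at the targets themselves is about 59% and 60%.
4. In sections 9.4.3.1 and 9.4.4.1, add exact confidence intervals for both rates. A 90% level matches section 9.4.1.

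The rates of 45% and 70% are already in the plan as examples; the sponsor should confirm that it regards them as unacceptable. No new desirable rates are needed.

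The cost is wording only. No patients, procedures or decision thresholds change, although the stated operating characteristics will look less favourable.
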